12.4. POWER CALCULATIONS

For the historical comparison analysis, assuming a two-sided test, 0.05 alpha level, baseline prevalence of 2 to 8%, and exclusion of 150 HPV vaccinated women from the analysis, we would have approximately 80% power to detect an absolute increase in overall HPV prevalence of at least 2 to 4% (see table below). Exploratory analyses of changes in HPV prevalence by gender and age and by vaccination status will be descriptive.

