7.2. HISTORICAL COMPARISON GROUP

95,000 tonsillectomy samples collected for the National Prospective Tonsillectomy Audit between 2003 -2004 have been archived by the Health Protection Agency (HPA) and now constitute an ethics approved research tissue bank called the National Anonymous Tonsil Archive (REC ref. 08/H0404/54). We will match the patients in our study with a sex and age matched cohort of approximately 1250 anonymised tonsillectomy samples from the above research tissue bank. Tissues from the anonymised tonsillectomy samples will be tested for HPV DNA by PCR and other techniques to provide a historical comparison group of HPV prevalence and distribution. The HPA have confirmed their approval to provide the tonsil samples, provided ethical approval is granted for our study.

If the above is not possible for any logistical reasons, then as an alternative, we may analyse an anonymised sample of up to 650 tonsil samples previously harvested in the PROTECT study in 2000-01, which are currently available to the Chief Investigator. The samples are totally anonymised, and so the only data available is the gender data and whether the age is below or above 9 years of age. These samples have equal numbers of males and females, and the age distribution between older than and younger than 9 years old is equally distributed. Ethics approval has been obtained by the PROTECT study to transfer the samples to our group for use in further ethically-approved studies.

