The rate of HPV persistence will be calculated as the proportion of baseline HPV-positive patients who again test HPV-positive in oral fluid, fingertip/nail brushings and urine samples collected after approximately 3 - 6 months. The rate of oral HPV infection clearance will be calculated as the proportion of baseline HPV-positive patients who test HPV-negative in oral fluid, fingertip/nail brushings and urine samples collected after approximately 3 - 6 months.

HPV incidence will be calculated as the proportion of baseline HPV-negative patients who test HPV positive in oral fluid, fingertip/nail brushings and urine samples collected after approximately 3 - 6 months. Exact 95% confidence intervals will be computed.

Multi variable regression models will be used to calculate the odds ratios of different risk factors for having HPV DNA in the tonsil and in the oropharynx, Variables to be included in the model (e.g. serological markers and clinical risk factors such as HPV vaccination status, tobacco and alcohol use) will be selected on the basis of descriptive statistics/possible causal relationship and/or a stepwise approach. Analysis of results may be performed to identify a possible marker or combination of markers for screening for persistent HPV infections in the oropharynx.

Among females in the target age class for vaccination (12 to 24 years), exploratory analyses will compare the HPV prevalence rate in HPV vaccinated and non HPV vaccinated patients using a Fisher's exact test. Association between HPV vaccine and oral HPV infection will be assessed using a case-control approach. Cases will be patients with HPV positive oral sample and controls will be patients with HPV negative oral sample. The exposure to vaccine will be compared between the case and the control groups using logistic regression, OR and its 95% confidence interval will be derived.

Prevalence of HPV in tonsils will be described and compared between the current cohort and the comparison historical cohort using a Cochran-Mantel-Haenszel test with stratification by age group and gender.

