12.3. SAMPLE SIZE CONSIDERATIONS

An analysis of current literature suggests that in a population recruited between 1990 and 2000, the prevalence of oral HPV was about 6.5%, varying from 0% - 10%. However, in an analysis of oropharyngeal scrapes and oral washings, the prevalence of HPV detection was much higher at 31%.

Pilot data of patients having tonsillectomy at University Hospital Coventry over two 3-month time periods are shown below in table 3. The number of tonsillectomy operations performed at the Heart of England NHS Foundation Trust - is approximately 50% of that for University Hospital Coventry quoted below.

Table 5: The number of tonsillectomy operations performed at University Hospital Coventry.

Age Group*	Number of Monthly recruitment (%)		
0-4	7 (12%)		
5-9	12 (20%)		
10-14	7 (12%)		
15-19	10 (17%)		
20-24	6 (10%)		
25-29	5 (8%		
30-34	4 (7%)		
35-39	5 (8%)		
40-44	1 (2%)		
45-49	1 (2%)		
50-69	1 (2%)		
Total	59		

^{*}There was an equal distribution of males and females in the group.

We plan to enrol 925 patients. The precision of the overall prevalence estimate that would be achieved with such a number is summarised in Figure 1 for prevalence ranging from 1 to 31 %. For example, if the observed prevalence is 10 %, the 95 % confidence interval for the overall population will be 8.4 to 11.8 % corresponding to a relative precision of 17 %.

[figure not shown]

Figure 1: Precision (95% confidence interval) of the prevalence estimate versus the prevalence observed in a random sample of 1250 patients.

We will also undertake a stratified sampling strategy to allow comparisons between those aged 14 and under (non-exposed, approximately one third of the cohort), and patients over 14 years of age (exposed) to allow the determination of the age of acquisition of infection and the optimal age of start of vaccination. The stratified sampling strategy will recruit patient subgroups as follows:

Table 6: The stratified sampling strategy for patient recruitment.

Age group	Sample size (%)		
0-4	150 (16.5%)		
5-9	150 (16.5%)		
10-14	150 (16.5%)		
15-19	150 (16.5%)		
20-24	150 (16.5%)		
25-34	100 (11%)		
35-44	60 (5.5%)		
45-65	15 (1.0%)		
Total	925		

[figure not shown]

Figure 2: Precision (95% confidence interval) of the prevalence estimate versus the prevalence observed in a random sample of 100, 150, and 250 patients.

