12.5. PLANNED INTERIM ANALYSIS

We will undertake an interim analysis when approximately 50% of the target recruitment has been achieved.

Table 7: Comparison Analysis.

Power	Alpha	Sample size historical cohort	Sample size Oromouth cohort	Prevalence historical cohort	Prevalence Oromouth cohort	Minimal detectable difference
0.80	0.05	1100	1100	2.0%	4.1%	2.1%
0.80	0.05	1100	1100	5.0%	8.1%	3.1%
0.80	0.05	1100	1100	8.0%	11.6%	3.6%

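### Table 7 powers the historical comparison on 1100 Oromouth patients, more than the study will enrol; at the current target, power is modestly below the tabulated 80 %

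*Protocol*

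**What the plan says.** Section 12.4 sets out the power for the comparison of tonsil HPV prevalence with the historical cohort, "assuming a two-sided test, 0.05 alpha level, baseline prevalence of 2 to 8" per cent. It continues with "exclusion of 150 HPV vaccinated women from the analysis, we would have approximately 80% power to detect an absolute increase in overall HPV prevalence", and puts that increase at 2 to 4 percentage points or more. Table 7, printed just after section 12.5, supports this with three rows. The column "Sample size Oromouth cohort" holds 1100 in each row, as does the historical column. The rows are 2.0 vs 4.1 %, 5.0 vs 8.1 % and 8.0 vs 11.6 %, each at 0.80 power.

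Section 12.3 states "We plan to enrol 925 patients", and the age strata in Table 6 add up to the same 925. The study summary speaks of up to 1000 prospective patients. The historical group is about 1250 sex- and age-matched archive samples (summary and section 7.2). If the archive cannot be used, "we may analyse an anonymised sample of up to 650 tonsil samples previously harvested in the PROTECT study".

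Section 12.2.2 says that prevalence will be "compared between the current cohort and the comparison historical cohort using a Cochran-Mantel-Haenszel test with stratification by age group and gender". It does not repeat the exclusion of vaccinated women.

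**The concern.** The Oromouth number in Table 7 exceeds the whole enrolment target, and section 12.4 then describes a further 150 patients as removed. No current recruitment figure in the protocol yields 1100, so the 80 % and the tabulated detectable differences describe a larger study than the one planned.

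Section 12.4 is the protocol's only power statement, and change in tonsil HPV prevalence over time is a listed secondary objective. Anyone judging what the comparison can show will rely on these figures.

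**Working it through.** **Inputs.** Two-sided alpha 0.05 and 150 exclusions (12.4); the prevalence pairs and 1100 per cohort (Table 7); 925 enrolled (12.3, Table 6); up to 1000 enrolled (summary); about 1250 historical samples (summary, 7.2).

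**Available Oromouth patients.** 925 − 150 = 775. 1000 − 150 = 850. If the exclusions shrink in proportion to enrolment (an assumption), 150 × 925/1250 = 111, leaving 814.

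**Origin of 1100.** 1250 − 150 = 1100. The protocol does not state this subtraction, but two remnants support it. The Figure 1 caption still refers to 1250 patients. The worked interval of 8.4 to 11.8 % at 10 % prevalence is the exact interval for 125/1250 (8.39–11.80 %); for 92/925 it is 8.09–12.06 %.

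**Formula.** With historical p1, n1, current p2, n2, d = p2 − p1 and p̄ the weighted mean prevalence:

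- SE0 = √[p̄(1 − p̄)(1/n1 + 1/n2)]
- SE1 = √[p1(1 − p1)/n1 + p2(1 − p2)/n2]
- Power = Φ[(d − c − 1.96·SE0)/SE1], with c = 0 uncorrected or c = ½(1/n1 + 1/n2) with continuity correction.

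**Reproducing Table 7, row 1 (1100/1100).** p̄ = 0.0305, SE0 = 0.00733, SE1 = 0.00732. Uncorrected: (0.0210 − 0.01437)/0.00732 = 0.906, power 81.7 %. With c = 0.00091: 0.782, power 78.3 %.

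**Same row at 1250/775.** p̄ = (25 + 31.775)/2025 = 0.02804, SE0 = 0.00755, SE1 = 0.00815. Uncorrected: (0.0210 − 0.01479)/0.00815 = 0.762, power 77.7 %. With c = 0.00105: 0.633, power 73.7 %.

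Power in %, uncorrected (continuity-corrected):

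| Historical / Oromouth | 2.0 vs 4.1 % | 5.0 vs 8.1 % | 8.0 vs 11.6 % |
|---|---|---|---|
| 1100 / 1100 (Table 7) | 81.7 (78.3) | 83.7 (81.4) | 81.1 (79.1) |
| 1250 / 775 | 77.7 (73.7) | 79.2 (76.5) | 76.2 (73.9) |
| 1100 / 775 | 75.3 (70.9) | 76.9 (74.0) | 74.0 (71.4) |
| 1250 / 850 | 79.6 (75.8) | 81.2 (78.7) | 78.3 (76.1) |
| 1250 / 814 | 78.7 (74.8) | 80.2 (77.7) | 77.4 (75.1) |

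The first row confirms that Table 7 is sound for its own inputs, so only the cohort size is at fault. Exact Fisher power lies between the two versions at 1250/775 (76.2, 78.2, 75.0 %) and at 1100/775 (73.6, 75.7, 72.8 %).

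**Difference detectable at 80 % power** (points, uncorrected to corrected):

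| Historical / Oromouth | Baseline 2 % | Baseline 5 % | Baseline 8 % |
|---|---|---|---|
| Table 7 as stated | 2.1 | 3.1 | 3.6 |
| 1250 / 775 | 2.18–2.30 | 3.14–3.25 | 3.79–3.90 |
| 1100 / 775 | 2.26–2.39 | 3.24–3.36 | 3.91–4.03 |

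**Conditional case.** If the 650-sample fallback were used against 775, power for the same differences would be about 56–65 %. Age would be known only as below or above 9 years, so the test would have two age bands. Section 12.4 makes no power claim for this case.

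All figures treat the comparison as two independent proportions and ignore the age and gender stratification of the planned test.

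**The case against.** The strongest reply is that the loss is small in the planned case. Section 12.4 claims only approximate power for a rounded range of 2 to 4 points. Against 1250 historical samples, 775 patients give 76–79 % uncorrected, with detectable differences of 2.2 to 3.8 points; 850 patients give 78–81 %. The figure of 775 also assumes that 150 exclusions still apply at the lower target. If nobody were excluded, 1250 vs 925 would give 80–83 % uncorrected (78–81 % corrected), close to Table 7. The comparison is secondary, and the primary prevalence estimate does not depend on Table 7.

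Most of this stands, and it limits the size of the point. It does not rescue the table, which states exact differences at 0.80 power for a cohort that cannot exist, and whose section assumes the exclusion.

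A reader might infer more than the documents support:

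- **Power in the 60s through 1:1 matching.** 775 vs 775 gives 62–69 %, but section 7.2 plans about 1250 matched samples and nowhere limits matching to one per patient.
- **A contradiction between 12.2.2 and 12.4 on vaccinated women.** The two can be read together: 12.4 says who leaves the analysis and 12.2.2 names the test. What is missing is a cross-reference.
- **A vaccine effect masking a rise over time.** This needs an effect on oral infection, for which section 1.5 says there are no data.

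**Conclusion.** The inconsistency is certain: 1100 analysable Oromouth patients cannot come from 925 or from 1000 enrolled. Its effect is modest. At 775 the tabulated 80 % becomes about 74–79 % against 1250 historical samples or 71–77 % against 1100. Detectable differences rise to about 2.2–2.4, 3.1–3.4 and 3.8–4.0 points. With 850 left, power is about 76–81 % against 1250, and with 814 about 75–80 %.

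The looser sentence in 12.4 nearly survives in the planned case; the exact entries of Table 7 do not. The result rests on 150 exclusions (or the scaled 111), on the historical number used, and on an unstratified calculation. It should be corrected, but as an error in a secondary comparison it does not undermine the main design.

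**What to change.** 1. Recompute Table 7 and the power sentence in 12.4 from the current target (say whether 925 or 1000), minus the number of vaccinated women now expected, against the historical number actually to be analysed. Name the calculation method.
2. In 12.2.2, state that the Cochran-Mantel-Haenszel comparison uses the population assumed in 12.4, with vaccinated women excluded.
3. Add one sentence that the 80 % statement does not apply if the 650-sample fallback is used.
4. In the same edit, bring the Figure 1 caption and the worked interval into line with the current target.

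The cost is a table and a few sentences, and the stated power becomes slightly less favourable. No patients, samples or tests are added.

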12.5. PLANNED INTERIM ANALYSIS

We will undertake an interim analysis when approximately 50% of the target recruitment has been achieved.

Table 7: Comparison Analysis.

Power	Alpha	Sample size historical cohort	Sample size Oromouth cohort	Prevalence historical cohort	Prevalence Oromouth cohort	Minimal detectable difference
0.80	0.05	1100	1100	2.0%	4.1%	2.1%
0.80	0.05	1100	1100	5.0%	8.1%	3.1%
0.80	0.05	1100	1100	8.0%	11.6%	3.6%

13. STUDY ORGANISATIONAL STRUCTURE

13.1. SPONSOR

This study will be sponsored by the University of Birmingham.

13.2. COORDINATING CENTRE

The study is being conducted under the auspices of the CRCTU and InHANSE, University of Birmingham according to their local standard operating procedures.

13.3. TRIAL MANAGEMENT GROUP

The Chief Investigator, Principal Investigators, Study Statistician, Senior Trial Manager and Study Coordinator will form the TMG. The TMG will be responsible for the day-to-day conduct of the study. They will be responsible for study set-up, promotion of on-going management of the study, monitoring patient accrual, the interpretation of the results and preparation and presentation of relevant publications.

13.4. TRIAL STEERING COMMITTEE

The TSC is made up of three representatives from GSK Biologicals (Funder), three Sponsor representatives and one independent member. The TSC will meet by mutual agreement on an as needed basis. The TSC will:

- Facilitate the research collaboration
- Address key study issues, including but not limited to:
 - Data analysis (including interim study results)
 - Interpretation
 - Publications

14. FINANCE

This is an investigator-initiated and investigator-led study funded by an educational grant from GSK Biologicals.

No individual per patient payment will be made to NHS Trusts, Investigators or patients.

15. ETHICAL CONSIDERATIONS

The study will be performed in accordance with the recommendations guiding physicians in biomedical research involving human subjects, adopted by the 18th World Medical Association General Assembly, Helsinki, Finland, 1964, amended by the 48th WMA General Assembly, Somerset West, Republic of South Africa, 1996 (website:http://www.wma.net/en/30publications/10policies/b3/index.html) (Appendix 2).

The study will be conducted in accordance with the Research Governance Framework for Health and Social Care, the applicable USTUDYK Statutory Instruments, (which include the Data Protection Act 1998 and Human Tissue Act 2008) and the Guidelines for Good Clinical Practice (GCP). The protocol will be submitted to and approved by the Research Ethics Committee (REC) prior to circulation.

Before any patients are enrolled into the study, the Principal Investigator at each site is required to obtain local Research and Development (R&D) approval. Sites will not be permitted to enrol patients until written confirmation of R&D approval is received by the OROMOUTH Study Office.

It is the responsibility of the Principal Investigator to ensure that all subsequent amendments gain the necessary local approval. This does not affect the individual clinicians' responsibility to take immediate action if thought necessary to protect the health and interest of individual patients.

16. CONFIDENTIALITY AND DATA PROTECTION

Personal data recorded on all documents will be regarded as strictly confidential and will be handled and stored in accordance with the Data Protection Act 1998. With the patient's consent/assent, their specific patient identifiers e.g. full name, date of birth, National Health Service (NHS) number, address, post code, hospital number, and GP details will be collected on the Patient Details Form.

Patients will be identified using only their unique RNO, initials, and date of birth on the CRF and correspondence between the OROMOUTH Study Office and the participating site. However patients are asked to give permission for the OROMOUTH Study Office to be sent a copy of their signed Informed Consent Form/Assent Form which will not be anonymised. This will be used to perform inhouse monitoring of the consent/assent process. The investigator must maintain documents not for submission to the OROMOUTH Study Office (e.g. Patient Identification Logs) in strict confidence. In the case of specific issues and/or queries from the regulatory authorities, it will be necessary to have access to the complete study records, provided that patient confidentiality is protected.

The OROMOUTH Study Office will maintain the confidentiality of all patient's data and will not disclose information by which patients may be identified to any third party other than those directly involved in the treatment of the patient and organisations for which the patient has given explicit consent/assent for data transfer (e.g. health and educational authorities to obtain HPV vaccination information). Representatives of the OROMOUTH study team may be required to have access to patient's notes for Quality Assurance (QA) purposes but patients should be reassured that their confidentiality will be respected at all times. The laboratories where sample analyses will be carried out will only identify samples by RNO. The research nurses will not have access to the result of the sample analyses.

17. INSURANCE AND INDEMNITY

University of Birmingham employees are indemnified by the University insurers for negligent harm caused by the design or co-ordination of the clinical study they undertake whilst in the University's employment.

In terms of liability at a site, NHS Trust and non-Trust hospitals have a duty to care for patients treated, whether or not the patient is taking part in a clinical study. Compensation is therefore available via NHS indemnity in the event of clinical negligence having been proven.

The University of Birmingham cannot offer indemnity for non-negligent harm. The University of Birmingham is independent of any pharmaceutical company, and as such it is not covered by the Association of the British Pharmaceutical Industry (ABPI) guidelines for patient compensation.

18. PUBLICATION POLICY

Results of this study will be submitted for publication in a peer reviewed journal. The manuscript will be prepared by the TMG and authorship will be determined by mutual agreement.

Any secondary publications and presentations prepared by Investigators must be reviewed by the TMG. Manuscripts must be submitted to the TMG in a timely fashion and in advance of being submitted for publication, to allow time for review and resolution of any outstanding issues. Authors must acknowledge that the study was performed with the support of University of Birmingham. Intellectual property rights will be addressed in the Clinical Study Site Agreement between Sponsor and site.

APPENDIX 1 - DEFINITION OF ADVERSE EVENTS

Adverse Event

Any untoward medical occurrence in a patient or clinical trial subject participating in the trial which does not necessarily have a causal relationship with the treatment received.

An AE can therefore be any unfavourable and unintended sign (including abnormal laboratory findings), symptom or disease temporally associated with the use of a medicinal product, whether or not related to the medicinal product.

Related Event

An event which resulted from the administration of any of the research procedures.

Serious Adverse Event

Any untoward medical occurrence or effect that at any dose:

- Results in death
- Is life-threatening*
- Requires hospitalisation** or prolongation of existing inpatients' hospitalisation
- Results in persistent or significant disability or incapacity
- Is a congenital anomaly/birth defect
- Or is otherwise considered medically significant by the Investigator***

Comments:

The term severe is often used to describe the intensity (severity) of a specific event. This is not the same as serious, which is based on patients/event outcome or action criteria.

- * Life threatening in the definition of an SAE refers to an event in which the patient was at risk of death at the time of the event; it does not refer to an event that hypothetically might have caused death if it were more severe.
- **Hospitalisation is defined as an unplanned, formal inpatient admission, even if the hospitalisation is a precautionary measure for continued observation. Thus hospitalisation for protocol treatment (e.g. line insertion), elective procedures (unless brought forward because of worsening symptoms) or for social reasons (e.g. respite care) are not regarded as an SAE.
- *** Medical judgment should be exercised in deciding whether an AE is serious in other situations. Important AEs that are not immediately life threatening or do not result in death or hospitalisation but may jeopardise the subject or may require intervention to prevent one of the other outcomes listed in the definition above, should be considered serious.

Unexpected and Related Event

An event which meets the definition of both an Unexpected Event and a Related Event.

Unexpected Event

The type of event that is not listed in the protocol as an expected occurrence.

APPENDIX 2 - WMA DECLARATION OF HELSINKI

Recommendations guiding physicians in biomedical research involving human subjects

Adopted by the 18th World Medical Assembly
Helsinki, Finland, June 1964
and amended by the
29th World Medical Assembly, Tokyo, Japan, October 1975
35th World Medical Assembly, Venice, Italy, October 1983
41st World Medical Assembly, Hong Kong, September 1989
and the

48th General Assembly, Somerset West, Republic of South Africa, October 1996

INTRODUCTION

It is the mission of the physician to safeguard the health of the people. His or her knowledge and conscience are dedicated to the fulfilment of this mission.

The Declaration of Geneva of the World Medical Association binds the physician with the words, "The Health of my patient will be my first consideration," and the International Code of Medical Ethics declares that, "A physician shall act only in the patient's interest when providing medical care which might have the effect of weakening the physical and mental condition of the patient."

The purpose of biomedical research involving human subjects must be to improve diagnostic, therapeutic and prophylactic procedures and the understanding of the aetiology and pathogenesis of disease.

In current medical practice most diagnostic, therapeutic or prophylactic procedures involve hazards. This applies especially to biomedical research.

Medical progress is based on research which ultimately must rest in part on experimentation involving human subjects.

In the field of biomedical research a fundamental distinction must be recognized between medical research in which the aim is essentially diagnostic or therapeutic for a patient, and medical research, the essential object of which is purely scientific and without implying direct diagnostic or therapeutic value to the person subjected to the research.

Special caution must be exercised in the conduct of research which may affect the environment, and the welfare of animals used for research must be respected.

Because it is essential that the results of laboratory experiments be applied to human beings to further scientific knowledge and to help suffering humanity, the World Medical Association has prepared the following recommendations as a guide to every physician in biomedical research involving human subjects. They should be kept under review in the future. It must be stressed that the standards as drafted are only a guide to physicians all over the world. Physicians are not relieved from criminal, civil and ethical responsibilities under the laws of their own countries.

I. BASIC PRINCIPLES

1. Biomedical research involving human subjects must conform to generally accepted scientific principles and should be based on adequately performed laboratory and animal experimentation and on a thorough knowledge of the scientific literature.

- 2. The design and performance of each experimental procedure involving human subjects should be clearly formulated in an experimental protocol which should be transmitted for consideration, comment and guidance to a specially appointed committee independent of the investigator and the sponsor provided that this independent committee is in conformity with the laws and regulations of the country in which the research experiment is performed.
- 3. Biomedical research involving human subjects should be conducted only by scientifically qualified persons and under the supervision of a clinically competent medical person. The responsibility for the human subject must always rest with a medically qualified person and never rest on the subject of the research, even though the subject has given his or her consent.
- 4. Biomedical research involving human subjects cannot legitimately be carried out unless the importance of the objective is in proportion to the inherent risk to the subject.
- Every biomedical research project involving human subjects should be preceded by careful
 assessment of predictable risks in comparison with foreseable benefits to the subject or to
 others. Concern for the interests of the subject must always prevail over the interests of
 science and society.
- The right of the research subject to safeguard his or her integrity must always be respected. Every precaution should be taken to respect the privacy of the subject and to minimize the impact of the study on the subject's physical and mental integrity and on the personality of the subject.
- 7. Physicians should abstain from engaging in research projects involving human subjects unless they are satisfied that the hazards involved are believed to be predictable. Physicians should cease any investigation if the hazards are found to outweigh the potential benefits.
- 8. In publication of the results of his or her research, the physician is obliged to preserve the accuracy of the results. Reports of experimentation not in accordance with the principles laid down in this Declaration should not be accepted for publication.
- 9. In any research on human beings, each potential subject must be adequately informed of the aims, methods, anticipated benefits and potential hazards of the study and the discomfort it may entail. He or she should be informed that he or she is at liberty to abstain from participation in the study and that he or she is free to withdraw his or her consent to participation at any time. The physician should then obtain the subject's freely-given informed consent, preferably in writing.
- 10. When obtaining informed consent for the research project the physician should be particularly cautious if the subject is in a dependent relationship to him or her or may consent under duress. In that case the informed consent should be obtained by a physician who is not engaged in the investigation and who is completely independent of this official relationship.
- 11. In case of legal incompetence, informed consent should be obtained from the legal guardian in accordance with national legislation. Where physical or mental incapacity makes it impossible to obtain informed consent, or when the subject is a minor, permission from the responsible relative replaces that of the subject in accordance with national legislation. Whenever the

- minor child is in fact able to give a consent, the minor's consent must be obtained in addition to the consent of the minor's legal guardian.
- 12. The research protocol should always contain a statement of the ethical considerations involved and should indicate that the principles enunciated in the present Declaration are complied with.

II. MEDICAL RESEARCH COMBINED WITH PROFESSIONAL CARE (Clinical Research)

- 1. In the treatment of the sick person, the physician must be free to use a new diagnostic and therapeutic measure, if in his or her judgement it offers hope of saving life, reestablishing health or alleviating suffering.
